19.1.2 Folic Acid

It is possible that AEs commonly associated with MTX treatment will occur. To minimize MTX toxicity, all subjects treated with MTX should be on folic acid or equivalent at a dose of at least 5 mg/week according to local guidelines and at the discretion of the investigator. Folic acid can either be given as a single dose weekly or be divided into daily doses to achieve at least 5 mg folic acid per week. It is the investigator's decision as to which dosing regimen is used.

19.1.3 Oral Corticosteroids

Oral corticosteroids are prohibited within 2 weeks prior to screening and during the entire treatment period and until the final visit (Visit 7). Refer to section 19.2 for treatment of asthma patients.

19.1.4 Nonsteroidal anti-inflammatory Drugs (NSAID)

Subjects may be treated with NSAIDs throughout the study. The choice and dose of NSAID used are at the discretion of the investigator, and the dose must be stable throughout the study. Adjustments to the dose or a change in NSAID may only be performed for safety reasons, and this change must be documented in the eCRF.

19.1.5 Non-NSAID Analgesics

Analgesics may be used for pain as required. However, subjects should not take analgesics within 12 hours prior to a visit where clinical efficacy assessments are performed and recorded. Adjustments to the analgesic regimen may only be made for safety reasons, but any change must be documented in the eCRF.

19.2 Prohibited Medicines

The following medications and therapies are not permitted during the trial and would require discontinuation of trial treatment:

- Oral, intramuscular, intravenous or intra-articular corticosteroids (permitted after week 5). (Asthma
 patients on stable prophylactic treatment are allowed to use an inhalation spray containing
 adrenocortical hormone. Furthermore, Beta-2 stimulating inhalants with short-term effects (SABA) are
 allowed for an asthma attack to an otherwise well-controlled asthma patient in the opinion of the
 investigator)
- Biologic therapies for RA
- Intravenous immunoglobulin therapy and/or plasmapheresis
- New therapies for RA should not be initiated during the trial. Initiation of any new immunosuppressant
 or immunomodulatory therapy would be considered a treatment failure and should result in withdrawal
 of the subject from the IMP.

Protocol Code Number: SynAct-CS002

As a signal for CYP1A2 induction has been observed at 10 μ M in a study with human hepatocyte the following CYP1A2 substrates are also prohibited:

- Alosetron
- Clozapine
- Flutamide
- Frovatriptan
- Melatonin
- Mexiletine
- mirtazapine
- Olanzapine
- Ramelteon
- Rasagiline
- Ropinirole
- Tacrine
- Theophylline
- Tizanidine
- Triamterene
- zolmitriptan

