16.3 Exclusion Criteria

Subjects meeting any of the following criteria are not eligible for participation in the study:

- 1. Participation in any other study involving investigational drug(s) within 4 weeks prior to study entry
- 2. Major surgery (including joint operation) within 8 weeks prior to screening or planned surgery within 1 month following randomization
- 3. Rheumatic autoimmune disease other than RA, including SLE, MCTD, scleroderma, polymyositis, or significant systemic involvement secondary to RA (e.g., vasculitis, pulmonary fibrosis or Felty's syndrome). Sjögren syndrome with RA is allowable
- 4. Functional class IV as defined by the ACR Criteria for Classification of Functional Status in RA or wheelchair/bedbound
- 5. Prior history of or current inflammatory joint disease other than RA (e.g., gout, reactive arthritis, psoriatic arthritis, seronegative spondyloarthropathy, Lyme disease)
- 6. Subjects with fibromyalgia
- 7. Initiation or change in dose for NSAIDs (including low-dose aspirin and COX-2 inhibitors) within 2 weeks prior to dosing with the IMP
- 8. Corticosteroids are prohibited within 2 weeks prior to screening (and during the entire treatment period and until the final visit (Visit 7)
- 9. Evidence of serious uncontrolled concomitant cardiovascular, nervous system, pulmonary (including obstructive pulmonary disease), renal, hepatic, endocrine (including uncontrolled diabetes mellitus), or gastrointestinal disease
- 10. Have prior renal transplant, current renal dialysis, or severe renal insufficiency (determined by a derived glomerular filtration rate (GFR) using Cockcroft Gault formula of ≤30 ml/min/1,73m² calculated by the local lab)
- 11. Uncontrolled disease states, such as asthma, psoriasis, or inflammatory bowel disease where flares are commonly treated with oral or parenteral corticosteroids
- 12. Evidence of active malignant disease (except basal cell carcinoma of the skin that has been excised and cured)
- 13. Pregnant women or nursing (breastfeeding) mothers
- 14. History of alcohol, drug, or chemical abuse within the 6 months prior to screening
- 15. Neuropathies or other painful conditions that might interfere with pain evaluation
- 16. Body weight of >150 kg.

EXCLUSION CRITERIA 17-20 ONLY APPLY FOR SUBJECTS IN NORWAY:

- 17. Evidence of moderate and/or severe organ dysfunction
- 18. Abnormal chest x-ray (as per the discretion of the investigator)
- 19. Evidence of positive hepatitis serology

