16.5.2 Discontinuation of Individual Subjects

The investigator may also withdraw a subject from the treatment or the study for any of the following reasons:

- If a subject who does not meet enrolment criteria is inadvertently enrolled
- · Enrolment in any other clinical trial with a study drug
- In case of severe worsening of symptoms, the investigator will be able to provide joint injections with corticosteroid as rescue medication. The use of local joint injections will be at the discretion of the investigator. The IMP/placebo treatment will continue as planned
- If the subject, for any reason, requires treatment with another therapeutic agent (rescue medication not included) that has been demonstrated to be effective for treatment of the study indication, discontinuation from the study occurs prior to the introduction of the new agent
- For medical or safety reasons
- If a female becomes pregnant

In case of early subject discontinuation and the reason for discontinuation (if it is known) will be registered in the eCRF and source documentation.

Protocol Code Number: SynAct-CS002

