19.3 Rescue Treatment

In case of severe worsening of symptoms, the investigator will be able to provide joint injections with corticosteroid as rescue medication. The use of local joint injections will be at the discretion of the investigator. The IMP/placebo treatment will continue as planned.

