  - Health Assessment Questionnaire (HAQ-DI)
  - C-Reactive Protein (CRP)

The Patient Global Assessment of Disease Activity RA, the Investigator Global Assessment of Disease Activity RA, and the CDAI score will be presented in absolute values and values relative to placebo by dividing the mean, median, min, and max values for each active treatment group by the corresponding value for the placebo group.

An indicator noting whether a subject received rescue treatment (joint injections with corticosteroid) during the 4-week treatment period (Baseline visit to Visit 6) will be constructed. The team will go

Study SynAct-CS002 – Statistical Analysis Plan

through the concomitant medication listings to define which subjects received rescue treatment before analyses.

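### Protocol 19.2 stops study drug after an intra-articular corticosteroid injection, while 19.3 and 16.5.2 allow the same injection as rescue with study drug continuing; the passages must be reconciled

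*Protocol*

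**What the plan says.** Protocol 19.2 opens its list with "The following medications and therapies are not permitted during the trial and would require discontinuation of trial treatment". The first item is "Oral, intramuscular, intravenous or intra-articular corticosteroids (permitted after week 5"), followed by an exception for inhaled treatment of asthma. There is no exception for rescue.

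Protocol 19.3 says that, after severe worsening, joint injections with corticosteroid may be given: "The use of local joint injections will be at the discretion of the investigator. The IMP/placebo treatment will continue as planned". Protocol 16.5.2 repeats this ("the investigator will be able to provide joint injections with corticosteroid as rescue medication"), with the same statement that study drug continues, but places it as a bullet in the list of reasons for withdrawing a subject. The next bullet, on other effective agents for the indication, exempts rescue medication.

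Exclusion criterion 8 (Protocol 16.3) reads "Corticosteroids are prohibited within 2 weeks prior to screening (and during the entire treatment period and until the final visit (Visit 7") and names no route. Protocol 19.1.3 gives nearly the same window but speaks of oral corticosteroids only.

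SAP 3.6 builds "An indicator noting whether a subject received rescue treatment (joint injections with corticosteroid) during the 4-week treatment period", from Baseline to Visit 6. SAP 6.1 summarises efficacy by treatment, by rescue received in that period, and in total.

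**The concern.** A site treating a worsening patient can find a rule that stops study drug and a rule that continues it. It cannot follow both. That is a conduct problem whatever the number of rescued subjects.

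The statistical consequence concerns week-4 CDAI, on which both parts of the primary efficacy endpoint rest. The trigger is severe worsening, so the affected subjects are selected on outcome and may be unevenly spread over the arms. Whether such a subject contributes a week-4 value, and whether that value was measured on or off study drug, can depend on the section the site applied. The arm summaries would then mix two ways of handling the same event.

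**Working it through.** **1. The passages side by side**

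| Place | Joint injection before the end of week 5 | Study drug |
|---|---|---|
| Protocol 19.2 | Not permitted | Discontinue |
| Protocol 19.3 | Allowed as rescue | Continues |
| Protocol 16.5.2 | Allowed as rescue (in the withdrawal list) | Continues |
| Exclusion criterion 8 | Corticosteroids barred until Visit 7, no route named | Not stated |
| Protocol 19.1.3 | Bars oral corticosteroids only, similar window | Not stated |
| SAP 3.6 and 6.1 | Expected, Baseline to Visit 6 | Not stated |

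**2. Can they be reconciled as written?**

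- *Timing.* Dosing runs from Day 1 to Day 28 (synopsis). The 19.2 restriction lifts only after week 5. Continuing study drug has meaning only while dosing is under way, so 19.3 operates wholly inside the period restricted by 19.2.
- *Exceptions.* The only exception in 19.2 is for inhaled asthma treatment. The rescue exemption in 16.5.2 belongs to its own bullet on other effective agents.
- *Cross-reference.* Neither 19.2 nor 19.3 mentions the other.

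**3. What follows for one injected subject**

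- *Following 19.2:* study drug stops. On premature withdrawal the final visit is 7 days after the last dose (Table 3, footnote 2) and End of Study procedures apply where possible (16.5.1). No off-drug week-4 visit is described. SAP 3.3 drops subjects with a missing value from analyses that need it and does not impute. A missing week-4 CDAI is therefore probable. It is an inference, because 19.2 itself speaks only of stopping treatment.
- *Following 19.3:* the subject stays on study drug and has a week-4 CDAI after the injection. CDAI includes the 28-joint swollen and tender counts (21.3.2).

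**4. The plan's own figures**

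The only planning figures for this endpoint are the confidence interval widths in Protocol 23.2. With 80% width probability,

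full width = 2 × t(0.975, n−1) × SD × √[χ²(0.80, n−1)/(n−1)] / √n.

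- n = 25, SD 3: 2.75 (stated: around 2.8).
- n = 30, SD 3: 2.47 (stated: around 2.5).
- n = 15, SD 2.5: 3.15 (stated: around 3.2).

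All three reproduce.

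**5. Illustration of size**

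The documents give no rescue rate and no response rate. Assume k rescued subjects in an arm of 30 (the planned minimum per group) and about 40% response in the rest.

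*Responder proportion.* The lower limit has no rescued subject responding, the upper limit all of them.

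| k | Rescued excluded | Included, none respond | Included, all respond |
|---|---|---|---|
| 3 | 11/27 = 41% | 11/30 = 37% | 14/30 = 47% |
| 6 | 10/24 = 42% | 10/30 = 33% | 16/30 = 53% |

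Against exclusion, inclusion moves the proportion by about −4 to +6 points for k = 3 and −8 to +12 points for k = 6.

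*Mean change.* Let D be the mean change of rescued subjects minus that of the others. Included minus excluded equals (k/30) × D. For an assumed D of ±5 points this is ±0.50 for k = 3 and ±1.00 for k = 6.

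*Precision.* Dropping the rescued widens the interval from 2.47 (n = 30) to 2.62 (n = 27) or 2.82 (n = 24).

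**The case against.** The strongest reply is that the documents lean towards one reading. Protocol 19.3 is a specific provision directly after a general list, 16.5.2 repeats it and exempts rescue from the neighbouring discontinuation rule, and SAP 3.6 and 6.1 plan for injections during treatment. This shows that the authors expected rescue. It does not remove the conflict, because 19.2 is itself specific: it names the intra-articular route and states an exception for something else.

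Several stronger conclusions are tempting, and the reply is right to resist them.

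- A reader might infer opposite week-4 data from identical patients. The contrast is between a probably missing value and a post-injection value. Protocol 16.5.2 separates withdrawal from treatment and withdrawal from the study, and nothing says that stopping under 19.2 cancels Visit 6.
- A reader might infer that the site's reading decides entry to the per-protocol set. Evaluability is settled and documented before the codes are broken (Protocol 23.1), at the Clean File meeting (SAP 1.6), with deviations weighed for severity and impact (SAP 3.10). What is missing is a stated criterion for rescue.
- A reader might take an assumed 5% to 20% share of rescued subjects as the shift in the responder proportion. It is the share affected; the shift is smaller.
- A reader might count exclusion criterion 8 as a clear bar on joint injections. It names no route, and 19.1.3 restricts a similar window to oral treatment. It adds ambiguity and no more.

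It is also true that efficacy is descriptive by arm, with no planned between-arm test, and that the by-rescue summaries make rescued subjects visible. They do not supply a week-4 value for a subject who stopped, nor say how a post-injection value should be read in the overall summary.

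**Conclusion.** The contradiction stands in the current text. For a corticosteroid joint injection during dosing, Protocol 19.2 stops study drug, while 19.3 and 16.5.2 continue it. Neither timing, the exemption in 16.5.2, nor the SAP's rescue indicator removes the conflict. This needs correcting at any rescue rate, because the instructions to sites cannot all be followed.

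The effect on the primary endpoint cannot be sized from the documents. Under the assumptions above it is about −4 to +6 percentage points on one arm's responder proportion with 3 of 30 rescued, and −8 to +12 with 6 of 30. Those limits require none or all of the rescued to respond and the whole arm to be handled one way; a split between sites gives less. They also rest on the inference that a stopped subject has no week-4 CDAI. Which clinical rule should apply is for the sponsor.

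**What to change.** - Reconcile Protocol 19.2, 19.3, 16.5.2 and exclusion criterion 8, read with 19.1.3, to one rule chosen by the sponsor on what happens to study drug after an intra-articular injection before Visit 7. State the routes to which each restriction applies.
- Move the rescue text in 16.5.2 out of the list of withdrawal reasons.
- State in SAP 3.2, consistently with that rule, whether rescue before Visit 6 is a major protocol violation for the per-protocol set.
- Before unblinding, identify subjects whose study drug was stopped because of an injection. The SAP 3.6 review of concomitant medication already finds the injections; what has to be added is whether dosing stopped as a result.

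The cost is a protocol wording amendment with the usual submission to the competent authority and ethics committee (Protocol 26.1.1), one SAP sentence and a letter to sites. No patients or procedures are added.

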19.3 Rescue Treatment

In case of severe worsening of symptoms, the investigator will be able to provide joint injections with corticosteroid as rescue medication. The use of local joint injections will be at the discretion of the investigator. The IMP/placebo treatment will continue as planned.

19.4 Treatment Compliance

Subject's compliance with study medication will be assessed at each visit. Every attempt will be made to select subjects who can understand and comply with instructions. Noncompliant subjects may be discontinued from the study at the discretion of the investigator. The sites will maintain drug accountability records and record the time and day of drug administration.

20 SCHEDULE OF VISITS

The schedule of visits and main procedures at each visit are summarized in the study flowchart below and are identical for Part 1 and Part 2.

Table 3: Study Flow Chart

Protocol Code Number: SynAct-CS002

	1	2	3	4	5	6	7	8
Visit	Screening	Baseline						EOS Safety follow- up call ²
Week	-2	0	1	2	3	4	5	8
Visit Window	-14 to -1d	Day 0	±1d	±1d	±1d	±1d	±1d	±3d
Informed consent	Х							
Randomization		X						
Demographics	Х							
Medical and surgical history	Х							
Inclusion/Exclusion criteria	Х	Х						
Pregnancy test (serum β-HCG)	Х							
Pregnancy test (dipstick)		Х	Х	Х	Х	Х	Х	
TB test ¹	Х							
Physical examination	Х						Х	
Vital signs	Х	Х	Х	Х	Х	Х	Х	
Height and weight ³	Х	Х	Х	Х	Х	Х	Х	
Concomitant medications	Х	Х	Х	Х	Х	Х	Х	
Concomitant therapy	Х	Х	Х	Х	Х	Х	Х	
Electrocardiogram (ECG)	Х	Х	Х	Х	Х	Х	Х	
X-ray of chest, hands, and feet	Х							
SJC and TJC	Х	Х		Х		Х	Х	
CDAI	Х	Х		Х		Х	Х	
Investigator Global VAS ⁵	Х	Х		Х		Х	Х	
Patient Global VAS	Х	Х		Х		Х	Х	
Patient Pain VAS	Х	Х		Х		Х	Х	
FACIT-Fatigue		Х		Х		Х	Х	
DAS28		Х		Х		Х	Х	
HAQ-DI (Health Assessment Questionnaire-Disability Index)		Х		Х		Х	Х	
SAEs/AEs		Х	Х	Х	Х	Х	Х	Х
Blood samples (biochemistry and TSH, T3, and T4)	х	х	х	х	х	Х	х	
Blood samples (hematology)	Х	Х		Х		Х	Х	
Blood sample (MC1R genotype analysis) ⁷		х						
HBsAg, HBV antibody & HCV antibody ⁴	Х							
PK (exposure)			Х	Х	Х	Х		
C-Reactive Protein (CRP)	Х	Х		Х		Х	Х	
RF or anti-CCP	Х							
Cytokines ⁶		Х		Х		Х		
Urinalysis	Х						Х	
Dispensing of IMP		Х	Х	Х	Х			
Accountability of returned IMP			Х	Х	Х	Х		

^{1:} QFG-IT (Mantoux test can be used if QFG-IT is not possible)

Protocol Code Number: SynAct-CS002

- 2: WD: Withdrawal. In case of prematurely subject withdrawal, the final visit should occur 7 days after the last IMP. Four weeks after the last IMP the subject will have a final safety follow-up call (EOS).
- 3: Height only at screening
- 4: Hepatitis B surface antigen (HBsAg), Hepatitis B virus (HBV), Hepatitis C virus (HCV)
- 5: Visual Analog Scale (VAS)
- 6: CXCL13, IL-1 β , IL-6, IL-10, and TNF- α
- 7: At baseline or any other visit after randomization

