14 EFFICACY ENDPOINTS

14.1 Primary Efficacy Endpoint

The change in CDAI after 4 weeks of treatment compared to baseline will be evaluated by assessing the following, by treatment group:

- Mean change in CDAI from baseline to week 4
- Proportion of subjects with a change in CDAI score from severe (CDAI > 22) to moderate (CDAI ≤ 22) at week 4 compared to baseline.

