16.5 Withdrawal

16.5.1 Subject may decide to withdraw

Subjects will be informed that they have the right to withdraw from the study at any time and for any reason without prejudice to his or her future medical care by the physician or the institution.

Subjects who prematurely discontinued from the study will not be replaced. The date for premature discontinuation will be recorded in the subject's source documents and electronic Case Report Form (eCRF).

If a subject is discontinued at any time after entering the study, the investigator should make a reasonable effort to ascertain the reason(s) while fully respecting the subject's rights, as a subject is not obliged to give a reason(s) for withdrawing. The investigator or site personnel should make every effort to contact the subject to assess his or her status and complete the termination page on the eCRF. In the case of subject discontinuation, the procedures described for the End of Study will be applied, where possible.

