20.1.6 Visit 6, 4. Week treatment Visit

The 4. Week Treatment Visit 28 days (±1 day) after the Baseline Visit. The following assessments will be performed:

- PK blood sample
- Vital signs (supine BP and heart rate)
- Changes in concomitant medication
- Changes in concomitant therapy
- 12-lead ECG
- Blood samples (hematology, biochemistry and TSH, T3, and T4)
- CRP
- Cytokines
- Pregnancy dipstick test
- Body measurements (weight)
- · Adverse event recording
- SJC and TJC
- CDAI
- Investigator Global VAS
- Patient Global VAS
- Patient Pain VAS
- FACIT-Fatigue
- DAS28
- HAQ-DI
- Accountability of returned IMP

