20.1.7 Visit 7, One-week post-treatment

The subject will return to the hospital for a final visit, 7 (±2 days) days after the last IMP has been taken. The following assessments will be performed:

- Pregnancy dipstick test
- Urinalysis (dipstick)
- Blood samples (hematology, biochemistry and TSH, T3, and T4)

Protocol Code Number: SynAct-CS002

- Vital signs (supine BP and heart rate)
- CRP
- Physical examination
- Body measurements (weight)
- · Adverse event recording
- Changes in concomitant medication
- Changes in concomitant therapy
- 12-lead ECG
- SJC and TJC
- CDAI
- Investigator Global VAS
- Patient Global VAS
- Patient Pain VAS
- FACIT-Fatigue
- DAS28
- HAQ-DI

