20.1.8 Final safety Follow-up Call and EOS

Investigator or study nurse will call the subject 4 weeks after the subject took the last IMP to follow-up on outstanding safety issues (AE/SAE).

21 Assessments, procedures, and Examinations

Subjects must provide written informed consent before any study-related procedures are performed.

Subject-related events and activities including specific instructions, procedures, concomitant medications, dispensing of study drug, and descriptions of AEs should be recorded in the appropriate source documents and the eCRF.

The schedule of assessments is provided in a study flow chart (Table 3) and is listed in Section 205. Unless otherwise specified, the investigator or accredited study personnel will perform all assessments.

Extra visits, examinations, tests, and interventions can be performed at any time if clinically indicated, as judged by the investigator.

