#### 3.3 Measurement Times, Missing Data, and Outliers

#### Measurement Times

The first date registered (screening visit) is to be used to define Baseline visit (Week 0 visit, within 14 days from screening). Week 1 visit is defined to be 7 days (±1 day) after Baseline, Week 2 visit 14 days (±1 day) after Baseline, Week 3 visit 21 days (±1 day) after Baseline, Week 4 visit 28 days (±1 day) after Baseline, final visit 7 (±2) days after the last investigational medicinal product has been taken, and visit 8 (end of study follow-up call) 4 weeks (±3 days) after the last investigational medicinal product has been taken, as described in protocol section 20.1. Any dates outside these visit windows are noted by the Data Manager during data validation as protocol deviations.

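### Subjects who stop study drug early but still consent are not told to attend the Day 28 assessment, and their final visit can fall before the week-4 window

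*Protocol*

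**What the plan says.** **Week 4 is counted from Baseline.** Protocol 20.1.6 has "The 4. Week Treatment Visit 28 days (±1 day) after the Baseline Visit", and SAP 3.3 agrees: "Week 4 visit 28 days (±1 day) after Baseline". The first primary efficacy measure in 14.1 is "Mean change in CDAI from baseline to week 4"; the second is the proportion moving from CDAI above 22 to 22 or below at the same time. The secondary and tertiary endpoints are also at week 4, and SAP 3.12 fixes ACR response there.

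**The final visit is counted from the last dose.** Protocol 20.1.7 states "The subject will return to the hospital for a final visit, 7 (±2 days) days after the last IMP has been taken". For withdrawals, Table 3 footnote 2 adds "In case of prematurely subject withdrawal, the final visit should occur 7 days after the last IMP", followed by a safety call at four weeks. The Visit 7 window is ±1 day in Table 3 but ±2 days in 20.1.7 and SAP 3.3.

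**CDAI is scheduled** at screening, baseline, week 2, week 4 and Visit 7 only.

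**Stopping drug is not always leaving the study.** Section 16.5.2 covers withdrawal from either. Section 19.1.1.1 discontinues study drug under the liver table, and 19.2 speaks of withdrawal from the study drug.

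**After discontinuation**, 16.5.1 says "In the case of subject discontinuation, the procedures described for the End of Study will be applied, where possible". Section 20.1.8, headed as the follow-up call and EOS, says "Investigator or study nurse will call the subject 4 weeks after the subject took the last IMP".

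**Analysis.** SAP 3.2 defines the efficacy set as all randomized and dosed subjects, labelled intention to treat. SAP 3.3 excludes subjects with a missing value from any analysis needing it and imputes nothing.

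**The concern.** While a subject takes all 28 doses the two clocks agree: Visit 6 is at Day 28 and the final visit about a week later. When drug stops early they separate, and the visit called final can come due before Visit 6. Nothing then tells the site whether Visit 6 still applies to someone willing to attend. A site following the stated timing would see such a subject about a week after the last dose and have only the telephone call left to make.

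What is at stake is selection rather than precision. Enrolment is already inflated for non-completion, so the planned completer numbers are protected. But stopping is plausibly related to tolerability or lack of effect, and an analysis set labelled intention to treat would at week 4 move towards a comparison of completers. A Day 28 assessment that was never made cannot be recovered by changing the SAP.

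**Working it through.** **Inputs.** Dosing Days 1 to 28 (synopsis); week-4 window Days 27 to 29 (20.1.6, SAP 3.3); final visit at last dose + 7 days, ±2 (20.1.7, SAP 3.3) or ±1 (Table 3); enrolment and completers from 15.1. The day on which subjects stop is not given and is an assumption below.

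**The plan's own figures.** 90/120 = 0.75 and 45/60 = 0.75, so the enrolment numbers imply 25% non-completion, a rate the current text does not state. The same rate gives 24/0.75 = 32 for Part 1 and 66/0.75 = 88 for Part 2, as planned. Planned non-completers are up to 120 − 90 = 30 in the main study and 60 − 45 = 15 in the sub-study.

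**Where the final visit falls.** For last dose on Day *d*, the final visit lies between *d* + 5 and *d* + 9 under the ±2 window.

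| Last dose | Nominal day | Range (±2) | Against Days 27–29 |
|---|---|---|---|
| Day 10 | 17 | 15–19 | before |
| Day 17 | 24 | 22–26 | before |
| Day 18 | 25 | 23–27 | reached only at the late limit |
| Days 20–22 | 27–29 | 25–31 | nominal day inside |
| Day 24 | 31 | 29–33 | reached only at the early limit |
| Day 25 | 32 | 30–34 | after, so Visit 6 is due first |

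The final visit cannot reach Day 27 when *d* + 9 ≤ 26, so *d* ≤ 17. Under ±1 day the condition is *d* + 8 ≤ 26, so *d* ≤ 18. On the nominal day it is *d* + 7 ≤ 26, so *d* ≤ 19.

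**Share of early stops affected.** An early last dose is on one of Days 1 to 27. On a favourable reading, the final visit is placed inside the week-4 window wherever its limits allow, and Visit 6 is attended whenever it comes due first.

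- Stops spread evenly: 17/27 = 63% (±2 days) to 19/27 = 70% (nominal day) have no in-window CDAI.
- Stops weighted early (weight 28 − *d*, total 378): 323/378 = 85% to 342/378 = 90%.
- Stops weighted late (weight *d*, total 378): 153/378 = 40% to 190/378 = 50%.

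These are shares of early stops under assumed timing, not counts of subjects.

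**End of Study, side by side.** Sections 15.7 and 20.1.8 and the last column of Table 3 use the term for a telephone call. Section 22.4 uses it, together with Early Termination, for the final visit. Section 21.1.4 requires a physical examination at early withdrawal, and the payment table in 27.1 puts withdrawal in the same row as the final visit, V7.

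**The case against.** **Footnote 2 concerns subject withdrawal, not stopping drug.** Visits 3 to 6 are timed from Baseline, and no passage cancels them when drug stops. This stands. A reader might infer that the protocol removes every early stopper from the schedule; it does not say so. What remains is a gap: 20.1.7 times a visit called final from the last dose for everyone, and no text says that Visit 6 survives.

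**Only a telephone call.** A reader might infer from 16.5.1 with 20.1.8 that a discontinued subject gets just a call. Footnote 2, 21.1.4, 22.4 and 27.1 all point to an in-person visit, so this is conflicting terminology and not a second pathway. It follows that the documents do not support saying a subject stopped for raised transaminases has no off-drug blood test. Visit 7 includes biochemistry, 19.1.1.1 recommends more frequent tests, and section 21 permits extra ones.

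**Counts.** It is tempting to apply the 63% to the 30 and 15 planned non-completers. That pool includes consent withdrawals and losses to follow-up, whom no schedule recovers. Section 16.5.2 also takes subjects needing another effective agent out of the study. The number who stop drug and still consent appears nowhere.

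**Tabulation.** A reader might infer that early final visits will be pooled with completers' week-5 data. The table specifications are a separate document (SAP Appendix 4), so this cannot be shown.

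**Phase and purpose.** This is a phase IIa trial with descriptive efficacy analysis, and following subjects after drug stops is partly a choice of estimand. That limits the weight of the point. But the SAP has chosen an intention-to-treat label, and the visit schedule does not secure the data that label needs. Some efficacy summaries are also by visit (for example 23.5.4), so not every efficacy output depends on week 4.

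**Conclusion.** The concern holds as a gap in data collection. The unsupported part of the schedule is definite: last doses on Days 1 to 17 under the ±2 window, or Days 1 to 19 on the nominal day. Whether this is most early stops depends on when they occur. It is under even or early-weighted stopping, but not under late-weighted stopping, where the share is 40% to 50%. All these shares assume that Visit 6 is attended whenever it precedes the final visit. The number of subjects who could be recovered is bounded above by 30 and 15 and is otherwise unknown. The meaning of End of Study in 16.5.1 is a separate inconsistency. Both are worth correcting because the change is cheap and the values cannot be obtained later; neither invalidates the design.

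**What to change.** 1. In 16.5, Table 3 footnote 2 and 20.1.7, separate stopping study drug from withdrawing from the study. State that subjects who stop drug early but still consent keep the Baseline-timed efficacy assessments (Visit 4 if still due, and Visit 6 at Day 28 ±1), in addition to the post-drug final visit.
2. Reconcile the use of End of Study across 15.7, 16.5.1, Table 3, 20.1.8 and 22.4, so that sites know which procedures apply after discontinuation.
3. Reconcile the Visit 7 window: ±1 day in Table 3, ±2 days in 20.1.7 and SAP 3.3.
4. In the SAP, label final visits after early stopping as early termination, so that they are not mixed with completers' week-5 data.

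The cost is protocol and SAP wording, plus one or two already designed visits for a minority of subjects. Some will decline, so the gap will narrow rather than close.
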